MINIMAL RISK CLINICAL RESEARCH PLAN

cphs v. 9/19/2019

Please complete: CPHS# 32008

PI: [name]

Important Note: The CPHS Department (Chair & Scientific) Review Form is required with this application. Find the form in the RAPPORT Library or on the CPHS Website.

- **DO NOT USE this form for retrospective chart review studies. Please use the Data Specimens Registries Research Plan.**
- **Respond to each item, even if to indicate N/A or not applicable**
- **Attach and/or upload this form as your 'Investigator Protocol' in Rapport**
- **If you are completing this form on a Mac, indicate your answer to any checkboxes by bolding or highlighting, or by deleting any incorrect options.**

1. Introduction and Background

The majority of opioid users meet criteria for anxiety and depressive disorders (Applebaum et al., 2010). However, many substance use disorder treatment programs do not offer treatment for co-occurring mental health problems (Watkins et al., 2004). The role of anxiety and depression also appears to be directly linked to opioid use itself. For instance, experimental research has shown that craving for opioids can be induced by depressed and anxious mood manipulations, suggesting a potential causal role between momentary anxious and depressed affect and daily craving among opioid users (Childress et al., 1994; Hogarth et al., 2019). Anxiety and depressive disorders also increase the likelihood of overdose among persons with OUD (OUD; Bartoli et al., 2014). Among persons who receive treatment for OUD, depression also predicts an increased risk of relapse (Kosten, Rounsaville, & Kleber, 1986).

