Urgent Need to Address Anxiety and Depression Comorbidity among Persons with OUD. Anxiety and depressive disorders frequently co-occur among persons with OUD. Moreover, research suggests that the presence of anxiety and depressive disorders among those with OUD are linked to a threefold risk of suicide attempts (Maloney, Degenhardt, Darke, & Nelson, 2009), compared to those with OUD alone. Among persons who receive treatment for OUD, depression also predicts an increased risk of relapse (Kosten et al., 1986). However, persons with OUD rarely seek treatment for anxiety or depressive disorders and often do not believe that they need treatment for either disorder despite meeting diagnostic criteria (Stein, Santiago Rivera, Anderson, & Bailey, 2017). Moreover, few substance use disorder treatment programs offer treatment for these co-occurring mental health problems (Watkins et al., 2004).

Potential Role of Anxiety and Depression in Influencing Opioid Use Behaviors. From a behavioral perspective, negative reinforcement of internal negative aversive states appears to be a strong driver of opioid use among persons with OUD (Blume, Schmaling, & Marlatt, 2000). This is exemplified by research examining the potential causal relationship between anxiety and depressive mood states and cravings among persons with OUD. For example, one study recruited 10 persons with OUD who had been abstinent for 30 days and randomized participants to either watch a depressive scene or be guided through self-hypnosis and found that opiate cravings increased from pre to post induction after the depressive scene exposure (Childress et al., 1994). Among persons receiving medication therapy for OUD ($N = 14$), another study found that an anxiety manipulation increased cravings from baseline, but a neutral manipulation condition had no significant effect on cravings (Hyman, Fox, Hong, Doebrick, & Sinha, 2007). Among 66 persons with OUD receiving medication treatment, participants who felt increased sadness in response to a video clip experienced increased cravings from pre to post, and this effect was moderated by anxiety (Stathopoulou, Pollack, & Otto, 2018). Lastly, another study showed that negative mood state manipulations were a trigger for heroin-seeking among persons with OUD (Hogarth et al., 2019). Taken together, these findings suggest that anxiety and depressive moods play a potential causal role in cravings and opioid use among persons with OUD.

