Main Study: Participants will complete the main consent form. Participants will complete self-report assessments on their anxiety symptoms, depressive symptoms, opioid cravings, and opioid use behaviors. Participants will be randomized to a smartphone-based digital intervention or waitlist control condition. The control group can receive the intervention once they have completed the one-month follow up section of the study if they would like it. The digital intervention will be designed to treat participants' anxiety and depressive symptoms, and participants will be asked to use the intervention four times per week for four weeks (16 digital sessions). Participants will complete post measures and one-month follow-up measures on anxiety symptoms, depressive symptoms, opioid cravings, and opioid use behaviors. The Precision Dx12-panel test cups (manufactured by American Screening Complete Drug Test Solutions) will be mailed to participants. Participants will also be asked to complete five urine tests to detect substance use (amphetamines, barbiturates, benzodiazepines, cocaine, ecstasy, marijuana, methamphetamine, opioids, oxycodone, and propoxyphene) across the study (1 at pre-digital intervention, 1 during the digital intervention, 1 post-digital intervention, 1 between post and follow-up of the digital intervention, and 1 at the 1-month follow-up of the digital intervention). Participants will be instructed when to complete each urine test and will be asked to take a photo of the back the label of each test showing the results to the experimenters and to text these photos to a Google Voice Number maintained by the experimenters. Both the digital intervention group and the control group will receive the same follow-up assessments and be asked for the urine samples. Following the study, the control group will be able to access the intervention and have access to the study team for support.

The Link for the intervention videos is below:

<https://drive.google.com/drive/folders/1aGv-d85VnuriTcta9dkRt6OjizcMHRf2?usp=sharing>

4. Analysis

Describe any qualitative tests and measures as well as quantitative methods:

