Writing Exposures (four virtual sessions). Based on a previous internet-based protocol, we will integrate writing exposures to treat participants' most significant fears (note that fears naturally occur in nearly all persons in the population even if the participant is not above clinical levels of anxiety). First, we will include a brief rationale for engaging in exposure therapy. Participants will then be asked to write about the nature of fears in detail, describing intimate fears and thoughts, writing in the first person and in present tense, relating olfactory, visual, and auditory sensations. The goal of this work is to provide a transdiagnostic ability to treat a variety of fears (e.g., this could target fears related to trauma, social anxiety, or interoceptive fears). **Cognitive-Reappraisal (four virtual sessions).** Participants will be educated about common principals of cognitive reappraisal in order to instill new insights. Participants will be asked to include positive aspects of trauma and aversive

experiences on their lives. Participants will also be asked to restructure their own thoughts. The platform will send reminder texts and emails when it is time to complete the new session. Additionally, the platform will also send targeted texts and emails to users who have not completed the intervention two days later and send a third text message and email asking if they were having any difficulty in accessing the intervention if they have not completed the intervention within three days after the scheduled time. **Qualitative Feedback.** In order to further refine the digital intervention, qualitative feedback on the digital intervention will also be solicited. This will include the participant's level of satisfaction with the intervention, perceived benefits, and recommended modifications, combining both Likert and open-ended feedback. **Refinement.** Following the conclusion of the study, the qualitative feedback and usage patterns will be used to further refine the intervention.

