There are no high risks or hazardous aspects of the proposed study. Nevertheless, we realize that interventions and assessments may promote increased focus on their mental health symptoms, compared to before they started the study. Research suggests that assessments are associated with *decreases* in MDD symptoms (Bakker & Rickard, 2018; Kauer et al., 2012). To date, the principal investigator has collected data from over 10,000 participants asking them to engage in anxiety and depressive interventions and experienced no known adverse events (Jacobson & Wilhelm, 2019). Given this, although there is a possibility that a subset of persons could react negatively to the intervention, it is also very unlikely to occur. Additionally, referrals for in-person treatment will be offered in the event of worsening suicidality or at the request of participants (see **Clinical Referrals below**). If any participant appears to be in crisis, appropriate action will be taken based on established suicide and crisis assessment protocols. Participants who report concerning levels of symptoms will be highlighted via algorithms as requiring contact and in-person referrals.

2. Adequacy of Protection Against Risks

a. Recruitment and Informed Consent

Recruitment. Recruitment will take place via Google Adwords and Reddit. **Informed consent.** The informed consent prior to the screen will provide information about the nature of the study in its entirety, including both information about the questions asked during the screen, data storage and retention plan, who will have access to this information, and responses to any participant questions. Participants will also be informed of the potential risks, benefits, and measures taken to protect participant confidentiality, and they will be provided an opportunity to ask questions about the study.

b. Protection against Risk

Protection of Privacy. Participants' privacy will be safeguarded by fully informed consent by informing participants what data will be collected, who will have access to this information, and how knowledge of how information collected will be utilized and disseminated (Ziegeldorf, García-Morón, & Wehrle, 2014).

Exclusion of High-Risk Populations. The current study will exclude persons who will be at high risk, specifically those with: (1) active suicidality, (2) psychosis, and (3) bipolar disorder. Treatment referrals will be made to those persons (see **Clinical Referrals below**).

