, the study team believes that referring participants to helpful resources is sufficient given the nature of the study. We will not be actively monitoring suicidality throughout the study and will only ask the PHQ-9 at certain points during the study. If participants give concerning responses when questionnaires are administered there will be an automated referral process to initiate resources if persons indicate high suicidal ideation.

Additionally, there is evidence that administering questionnaires such as the PHQ-9 do not increase an individual's likelihood of suicidality. We do not believe that our study questionnaires will increase this likelihood. Again, anyone indicating suicidality in the screening questionnaires will not be eligible for the study. As we are mainly concerned with Opioid Use in our study demographic, we do not anticipate too many participants in our 80 person sample indicating high suicidal ideation, believe that our referral process will be sufficient.

b. Confirm that risks to subjects have been minimized, by use of procedures which are consistent with sound research design and which do not unnecessarily expose subjects to risk:

The study teams believes that they have taken the necessary precautions to ensure the safety of our participants.

Protection of Privacy. Participants' privacy will be safeguarded by fully informed consent by informing participants what data will be collected, who will have access to this information, and how knowledge of how information collected will be utilized and disseminated.¹²⁹ All participants must demonstrate comprehension (full understanding of study details), competence (ability to provide consent), and voluntariness (consent of their own volition) based on their phone calls with the postdoctoral fellow. Following suggestions for fully addressing privacy concerns in digital phenotyping studies, consent will be obtained through verbal discussion with a postdoctoral fellow

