Clinical Referrals. All participants will be given the phone number for the National Suicide Prevention Hotline, which is funded by the Substance Abuse and Mental Health Services Administration (SAMHSA). The hotline is staffed 24/7 by licensed mental health providers and is available throughout the United States. For persons not in acute risk who need a referral to outpatient treatment, we will identify referral sources using the Anxiety and Depression Association of America (ADAA), the Association for Behavioral and Cognitive Therapies (ABCT), the American Psychiatric Association, and the American Psychological Association. Each of these organizations maintains an active registry of current psychologists and psychiatrists across the country, many of whom provide the ability to also specify persons specializing in treating MDD. Participants in acute psychiatric emergencies will be directed to travel to their nearest emergency room,

Plan to Report any Participants Experiencing Potential Crisis:

All incidents of participants experiencing potential crises where follow-up is required will be reported within a week via email to CPHS, including a description of the action taken.

c. Describe why all the risks to subjects are reasonable in relation to both anticipated benefits and the knowledge expected to be gained from the study:

3. Potential Benefits of the Proposed Research to Human Subjects and Others

There are several potential benefits of the proposed research. Participants may experience reductions in their anxiety and depressive symptoms, as well as decreased cravings and reduced opioid use behaviors. In addition, there are also some salient potential benefits to other persons with anxiety and depressive disorders and OUDs based on the results from this work. In particular, this work could foster the ability to deliver behavioral treatments with little cost to persons needing treatment.

4. Importance of the Knowledge to be Gained

The knowledge to be gained from the proposed project has substantial public health importance. Anxiety and depressive disorders are common, severely disabling, and costly conditions. Thus, the current proposal will fill a crucial gap in knowledge regarding whether technology-based interventions for anxiety and depressive disorders might be used to improve treatment among persons receiving medication treatment for OUDs.

7. Unexpected Events or Incidental Findings

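### No named scheduled measure asks about overdose, suicide attempt, emergency care or admission, so harms may be under-counted and may be ascertained unequally by arm

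*Combined protocol and SAP*

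**What the plan says.** All references are to the combined protocol and SAP.

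- **Hazards of the population.** Section 1, Introduction and Background: "Anxiety and depressive disorders also increase the likelihood of overdose among persons with OUD". Under A. Significance, anxiety and depressive disorders in people with OUD "are linked to a threefold risk of suicide attempts".
- **Study risks.** Section 6, Potential Risks, opens with "There are no high risks or hazardous aspects of the proposed study". It then accepts that a subset of participants could react negatively, though it thinks this very unlikely. The paragraphs on withdrawal in sections 6 and 7 give hospitalisation as an example of a deteriorating course.
- **Scheduled data.** Section 3, Main Study: "Participants will complete post measures and one-month follow-up measures on anxiety symptoms, depressive symptoms, opioid cravings, and opioid use behaviors". Five urine tests are added, and both arms get the same follow-up assessments. Section 4, Measures, names the instruments, but none for opioid use behaviors.
- **Safety monitoring.** Section 6: "We will not be actively monitoring suicidality throughout the study and will only ask the PHQ-9 at certain points during the study". High ideation on a questionnaire starts an automated referral, and algorithms flag concerning symptom levels for contact.
- **Reporting.** Section 6, plan for participants in potential crisis: "All incidents of participants experiencing potential crises where follow-up is required will be reported within a week via email to CPHS".
- **Session messages.** Section 4, Technology-Based Digital Intervention: a reminder when each session falls due, a second round two days later if it is not done, and after three days the platform will "send a third text message and email asking if they were having any difficulty in accessing the intervention". Controls can have the sessions only after the one-month follow-up.

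**The concern.** Section 6 fixes what happens once a crisis is known. It does not fix how one becomes known, and the analysis paragraph in section 4 does not mention harms. If no form asks about an event, a low count cannot be told apart from a failure to ask. One arm also has more contact with the study during the comparison, so it has more occasions on which something might be volunteered.

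At stake is whether this trial of a prototype, which includes written exposure to participants' most significant fears and is meant to lead to a larger proposal, can produce a usable harms table. A count of zero would be hard to interpret, and an imbalance between arms could reflect ascertainment.

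**Working it through.** The plan states no harm rate or detection rate, so there is no figure of its own to reproduce. The check sets the text side by side, counts contacts by arm, and then shows what incomplete capture does to a zero count.

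**1. Events against measures.**

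| Event | Where the plan raises it | Named scheduled measure that records it |
|---|---|---|
| Overdose | Section 1 | None |
| Suicide attempt | A. Significance | None; the PHQ-9 route responds to ideation |
| Negative reaction to the intervention | Section 6, Potential Risks | None; symptom scales show level, not attribution |
| Emergency care, admission | Sections 6 and 7 | None |

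Relapse, which the plan also raises, is covered by the urine tests.

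**2. Scheduled contacts common to both arms.** Section 14 lists 3 paid questionnaires (pre, post, one month) and 5 urine tests (weeks 0, 2, 4, 6, 8). Payment is 3 × $15 + 5 × $15 = $120, which agrees with section 13, so the contact schedule is read correctly.

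**3. Session messages.** There are 16 sessions.
- Minimum, every session done promptly: 16 × 1 = 16 rounds.
- Maximum, every session still undone after three days: 16 × 3 = 48 rounds.
- Controls up to the one-month follow-up: 0.
- Messages in either arm that ask about a harm: 0.

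**4. What a zero count would mean.** Let r be the true risk per participant, d the share of events that reach the team (taken as equal in both arms here) and n = 40 per arm (Hypothesis 1). The chance of recording none in an arm is (1 − r × d)^n. All values of r and d are assumptions, shown as a range.

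| True risk r | Expected events, 40 × r | P(none recorded), d = 100% | d = 60% | d = 30% |
|---|---|---|---|---|
| 2% | 0.8 | 0.98^40 = 0.45 | 0.988^40 = 0.62 | 0.994^40 = 0.79 |
| 5% | 2 | 0.95^40 = 0.13 | 0.97^40 = 0.30 | 0.985^40 = 0.55 |
| 10% | 4 | 0.90^40 = 0.01 | 0.94^40 = 0.08 | 0.97^40 = 0.30 |

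**5. Limit with complete capture.** The one-sided 95% upper limit after zero events is 1 − 0.05^(1/n). For 40 per arm it is 1 − 0.05^(1/40) = 7.2%. For the 30 per arm given in Aim 2 it is 1 − 0.05^(1/30) = 9.5%. These limits apply only if every event is captured.

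**6. Comparison between arms.** The recorded risk ratio equals the true risk ratio × (detection share, intervention ÷ detection share, control). With equal true risks it is simply the ratio of detection shares. The documents give neither share, so no size can be attached. If detection is equal, the ratio is 1.0: events are under-counted, but not differently by arm.

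**The case against.** The case on the other side has real weight.

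- **Background hazards.** Overdose and suicide attempt appear as hazards of the population, not as study risks in section 6. That is correct. They remain events that a harms table in this population would be expected to contain.
- **Existing channels.** The PHQ-9 referral and the symptom flags are not limited to one arm, a flag leads to contact, and every participant is told how to reach the investigators in an emergency. This stands as far as it goes: the plan does collect an ideation signal, on the same forms in both arms. It does not record events.
- **Silence is not absence.** The unnamed measure of opioid use behaviors could contain an overdose item. The phone assessments by a postdoctoral fellow in section 6 have no stated content or schedule after randomisation. The qualitative feedback on the intervention is partly open-ended. None can be ruled out, so the claim is limited to named measures.
- **The messages ask about access, not health.** True, and 48 rounds would need every session to lapse. A reader might infer that harms will certainly be counted differently by arm, or that the intervention arm will show a specific excess. The documents support neither. Any such multiple only restates assumed detection shares.
- **No safety claim is planned.** The hypotheses concern feasibility, acceptability and efficacy. The statement that participants "experienced no known adverse events" refers to the investigator's previous work, not to a conclusion planned for this trial. A reader should not take it as one. What remains is that this trial could end with a similar statement without having asked.

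**Conclusion.** The point holds in a limited form. No named scheduled measure asks about overdose, suicide attempt, emergency care, admission or distress from the sessions, and the plan does not say how reportable crises are found. Such events would be known mainly by spontaneous report, so under-counting is likely. Unequal ascertainment is a credible possibility because 16 to 48 rounds of session messages go to one arm and none to the other, but its size is unknown and its presence is not shown.

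This rests on two readings: that the unnamed opioid-use measure and the phone assessments do not already ask these questions, and that extra contact may prompt extra reporting. If the first is wrong, the remedy is to name those instruments. The stronger inference that suicidality goes unmonitored is not supported: the plan explains its choice to rely on the PHQ-9 at set points with automated referral, and this point does not ask for that to change. The efficacy analysis is not affected.

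**What to change.** 1. Add one short yes/no block with dates to the existing pre, post and one-month Qualtrics forms, identical in both arms: overdose, suicide attempt, emergency visit, hospital admission, stopping OUD medication, distress attributed to the study. The pre form supplies the baseline; the other two ask about the time since the last form.
2. Record the source of each reported event: scheduled question, symptom flag or spontaneous report.
3. Add a sentence to the analysis paragraph in section 4: harms are tabulated by arm, with the number of participants who answered, and the scheduled-question count is the main comparison. Events from other sources are listed separately.
4. If the opioid use behaviors measure or the phone assessments already ask these questions, name them, state when they are given, and apply them identically in both arms.

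**Cost.** A minor amendment to forms already in use and already paid at $15 each, so no new payment is needed. Participants spend a few more minutes, and the team has some extra follow-up of positive answers. No additional time points are needed, and the rule for reporting to CPHS can stay as it is. The change is easy before enrolment; events that were never asked about cannot be reliably recovered afterwards.
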